8.4.3 TOXICITY MANAGEMENT

Whether or not considered treatment related, all subjects experiencing AEs must be monitored periodically until symptoms subside, any abnormal laboratory values have resolved or returned to baseline levels or they are considered irreversible, or until there is a satisfactory explanation for the changes observed.

In the combination cohorts, in cases where a toxicity cannot be clearly attributed to either drug (ZN-c5 or palbociclib), ZN-c5 should be modified or discontinued first.

8.4.3.1 DOSE LEVELS FOR TREATMENT MODIFICATION

ZN-c5

ZN-c5 dose levels for intra-subject treatment modification in the Monotherapy and Combination Dose Escalation will become available as dose levels are being assessed.

ZN-c5 dose levels for treatment modification in the Monotherapy Expansion and Combination Phase 2 are provided in Table 8.

Table 8: ZN-c5 Dose Levels for Treatment Modification in Monotherapy Expansion and Combination Phase 2

Dose Level	Dose of ZN-c5
1	RP2D and schedule from the Monotherapy and Combination Dose Escalation ^a
- 1	-25%, further to be determined based on the Dose Escalation data
- 2	-50%, further to be determined based on the Dose Escalation data

RP2D = recommended Phase 2 dose

Dose Level 1 will be the RP2D or a lower dose from the Monotherapy and Combination Dose Escalation according to the information including the safety, PK, pharmacodynamic and/or preliminary efficacy data.

Subjects who are unable to tolerate ZN-c5 at the lowest dose level should be permanently discontinued from study drug, unless the Investigator considers continuation of treatment at a lower dose to be in the best interest of the subject and the Sponsor's Medical Monitor or designee approves further dose reduction.

Palbociclib

Please follow safety guidelines in the most recent local or US Full Prescribing Information for palbociclib (IBRANCE®, Pfizer Inc.).

8.4.3.2 DOSE ADJUSTMENT OF PALBOCICLIB

For subjects participating in the combination therapy portion of the study with toxicity potentially attributable to palbociclib, please follow safety and toxicity guidelines in the most recent local or US Full Prescribing Information for palbociclib (IBRANCE®, Pfizer Inc.).

Dose holds for reasons other than toxicity (e.g., scheduled surgery) are allowed for up to 21 days. Dose holds for reasons other than toxicity that last more than 21 days require that the subject be removed from study unless deemed in the best interest of the patient to continue and after discussion between the Investigator and the Sponsor's Medical Monitor (Section 7.2).

Unmanageable AEs attributed to palbociclib alone may result in continuation of single agent ZN-c5 therapy as long as none of the treatment discontinuation criteria are met (Section 7.2).

If treatment with ZN-c5 is discontinued, on-study treatment with palbociclib can be continued per protocol unless palbociclib is commercially available and treatment is reimbursed for the patient, then the patient can come off study treatment.

8.4.3.3 DOSE ADJUSTMENT OF ZN-C5

ZN-c5 will be held for any ZN-c5 related Grade ≥ 3 adverse event or any DLT.

ZN-c5 dosing may be restarted if the AE that resulted in the dose hold resolves to \leq Grade 1 (or baseline) within 21 days. If the toxicity does not resolve to \leq Grade 1 or baseline within 21 days, ZN-c5 will be permanently discontinued, unless deemed in the best interest of the patient to continue and after discussion between the Investigator and the Sponsor's Medical Monitor (Section 7.2).

Dose holds for reasons other than toxicity (e.g., scheduled surgery) are allowed for up to 21 days. Dose holds for reasons other than toxicity that last more than 21 days require that the subject be removed from study unless deemed in the best interest of the patient to continue and after discussion between the Investigator and the Sponsor's Medical Monitor (Section 7.2).

Doses withheld during a cycle will not be made up. When a dose reduction is required because of AEs/DLTs, no dose re-escalation will be permitted for the duration of study treatment unless mutually agreed upon by the Investigator and Sponsor.

For dose modifications based on the occurrence of ZN-c5 related AEs, see Table 9. Up to 2 dose reductions are allowed.

Table 9: Dose Reduction Criteria ZN-c5: All Phases

Dose Reduction Criteria	Dose Adjustment
Grade 4 (< 0.5 × 10 ⁹ /L) neutropenia lasting ≥ 8 days	
Febrile neutropenia requiring antibiotics	Reduce 1 dose level or discontinue treatment if
Grade 4 (< 25×10^9 /L) thrombocytopenia or Grade 3 (≥ 25 to < 50×10^9 /L) thrombocytopenia associated with Grade ≥ 3 bleeding and/or requiring platelet transfusions	occurring at the lowest dose level possible (which is 50 mg/day in the Dose Escalation Cohorts or Dose Level -2 in the Monotherapy Expansion/Phase 2 and Combination Phase 2) ^b
Any non-hematologic Grade 3 toxicity a, c	
Any non-hematologic Grade 4 toxicity ^c	Discontinue treatment ^b

- ^a Grade 3 nausea, vomiting, diarrhea, or constipation for < 48 hours do not require a dose reduction.
- If it is in the best interest of the subject to continue treatment in the opinion of the Investigator and after discussion with the Sponsor, the subject can continue treatment at a (further) reduced dose level.
- Includes laboratory values deemed clinically significant by the Investigator

If the ZN-c5 dose is reduced, the dose will not be increased again. If a benefit/risk assessment favors the increase of dose up to the initial starting dose after dose reduction, an agreement with the Sponsor's Medical Monitor is required prior to the dose increase.

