7 STUDY INTERVENTION DISCONTINUATION AND PARTICIPANT DISCONTINUATION/WITHDRAWAL

7.1 DISCONTINUATION OF STUDY INTERVENTION

Discontinuation from investigational treatment does not mean discontinuation from the study, and remaining study procedures should be completed as indicated by the study protocol (unless withdrawal of consent by the subject).

Subjects should have an End of Treatment Administration Visit as soon as possible (within 7 days) after the decision is made to discontinue study treatment (Section 7.4).

Subjects will return or will be contacted for a Safety Follow-up Visit 30 days (± 7 days) after the last dose of ZN-c5 taken (Section 7.5).

Subjects without PD at the time of study drug discontinuation will continue to undergo a Disease Assessment Follow-up Visit every 12 weeks (± 7 days) (Section 7.6).

Subjects will be followed for survival and subsequent breast cancer therapies.

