7.2 PARTICIPANT DISCONTINUATION/WITHDRAWAL FROM TREATMENT AND FROM THE STUDY

Subjects may be discontinued from the investigational treatment in the following situations:

- Documented progression of disease or clinical progression
- Death
- Investigator discretion
- Non-compliance with study drug or protocol
- Important protocol deviation
- Pregnancy
- Patient discretion
- Withdrawal of consent (subjects are free to withdraw participation at any time)
- Lost to follow-up
- Subjects incorrectly initiated on study treatment
- Intercurrent illness that would, in the judgment of the investigator, affect assessments of clinical status to a significant degree
- Unacceptable toxicity
- Liver testing abnormalities meeting Hy's Law criteria (See Section 10.4.7)
- Study termination by the Sponsor

Subjects who are withdrawn from the study but are evaluable will not be replaced. Any subject who is withdrawn and is not evaluable may be replaced to ensure a minimum number of evaluable patients.

Subjects may withdraw from any aspect of the voluntary exploratory research at any time, without prejudice to further treatment and independent of any decision concerning participation in other aspects of the study.

If there is strong evidence of clinical benefit and reasons to justify continuation of the study drug, even though treatment discontinuation criteria have been met, this decision must be reviewed with the Sponsor, and continuation of therapy may be allowed assuming all other treatment resumption criteria have been met.

Subjects will be discontinued from the study in the following situations:

- Death
- Lost to follow-up
- Withdrawal of consent
- Study end per protocol
- Early study termination by Sponsor

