7.3 LOST TO FOLLOW-UP

A participant may be considered lost to follow-up if they fail to return for 2 consecutive scheduled visits and is unable to be contacted by the study site staff.

The following actions must be taken if a participant fails to return to the clinic for a required study visit:

- Attempt to contact the participant and reschedule the missed visit
- Counsel the participant on the importance of maintaining the assigned visit schedule
- Ascertain if the participant wishes to and/or should continue in the study.

Prior to determining that a participant is lost to follow-up, the investigator or designee will make every effort to regain contact with the participant (e.g., at least 3 telephone calls and, if necessary, a certified letter to the participant's last known mailing address). Contact attempts should be documented in the participant's medical record or study file.

Participants who are unreachable based on the attempts outlined above will be considered to have withdrawn from the study with a primary reason of lost to follow-up.

If study drug is discontinued due to subject decision, the subject may elect to continue with treatment discontinuation assessments, safety follow-up and additional follow-up, if applicable.

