7.6 DISEASE ASSESSMENT FOLLOW-UP VISITS

Subjects without PD at the time of study drug discontinuation will continue to undergo disease evaluations every 12 weeks ± 7 days until confirmation of PD, initiation of the first subsequent cancer therapy, withdrawal of consent, death, loss to follow-up, or until the study is terminated.

Once a subject has confirmation of PD or has initiated subsequent cancer therapy, whichever occurs first, follow-up will discontinue.

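### The 21-day rule for non-toxicity dose holds (Protocol 8.4.3.2 and 8.4.3.3) removes subjects from the study, against the follow-up rules in 7.1, 7.2, 7.6 and 9.4.5.4

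*Protocol*

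**What the plan says.** Sections 8.4.3.2 and 8.4.3.3 of the Protocol carry the same sentence. Holds for reasons other than toxicity, such as scheduled surgery, are allowed for up to 21 days. Those that "last more than 21 days require that the subject be removed from study unless deemed in the best interest of the patient to continue", as agreed between the Investigator and the Medical Monitor. Both sentences refer to Section 7.2.

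The toxicity rule in 8.4.3.3 uses the same 21 days with a different consequence. If the event has not resolved to Grade 1 or lower "or baseline within 21 days, ZN-c5 will be permanently discontinued", with a similar exception.

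The general rules are in Section 7:

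- **7.1:** "Discontinuation from investigational treatment does not mean discontinuation from the study". The section also says: "Subjects will be followed for survival and subsequent breast cancer therapies".
- **7.2:** separate lists for stopping treatment and for leaving the study. The study list has five entries: death, loss to follow-up, withdrawal of consent, study end per protocol, and "Early study termination by Sponsor".
- **7.3:** where the subject decides to stop the drug, "the subject may elect to continue with treatment discontinuation assessments, safety follow-up and additional follow-up, if applicable".
- **7.6:** "Subjects without PD at the time of study drug discontinuation will continue to undergo disease evaluations every 12 weeks", until progression, new cancer therapy, withdrawal of consent, death, loss to follow-up or study termination.

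Protocol 9.4.5.4 adds that, for PFS, subjects who stop treatment before progression are still followed to objective progression.

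**The concern.** The protocol separates leaving treatment from leaving the study, and its efficacy follow-up depends on that separation. The dose-hold sentence crosses the line: a hold for a non-medical or surgical reason becomes a reason to leave the study, although 7.2 does not list it. On the literal text, a subject whose hold for scheduled surgery overruns by a day leaves the study, while a subject with an unresolved Grade 3 toxicity loses only the drug and stays in follow-up.

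The stake is outcome data after the hold. The subject has been dosed, so remains in the Full Analysis Set and in the CBR denominator. What is lost is the later scans and survival contacts. CBR is the primary endpoint of both Phase 2 parts, and stable disease counts only if it lasts 24 weeks. Under 7.2, subjects who are withdrawn but evaluable are not replaced.

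**Working it through.** The plan gives no figure to reproduce. The check is a comparison of texts, followed by a small date calculation showing which holds could matter.

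**Comparison of texts**

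1. Is a long hold a study-exit reason? 8.4.3.2 and 8.4.3.3: yes, unless continuing is agreed. The five entries in 7.2: no.
2. Does stopping the drug end disease follow-up? 8.4.3.2 and 8.4.3.3, read literally: yes. 7.1, 7.6 and 9.4.5.4: no. None of the stopping events in 7.6 is a dose hold.
3. Does it end survival follow-up? Read literally: yes. 7.1 says subjects will be followed. Section 7.7 starts survival contacts only at confirmed progression or first new therapy, so a subject with stable disease would reach it through 7.6. Removal from the study cuts off both.
4. What was probably meant? Both sentences cite 7.2, where the exception for clinical benefit concerns the drug: "continuation of therapy may be allowed assuming all other treatment resumption criteria have been met". Section 8.4.3.2 also speaks elsewhere of coming off study treatment, so the narrower wording was available. This points to removal from treatment as the intent, but the operative words say something else.

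**Effect on the endpoints if applied literally**

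- *CBR (SAP 6.5.2).* Without progression or death, the duration of stable disease ends at the last assessment showing it. The 24-week threshold, with its one-week window, is 23 × 7 = day 161, counting first dose as day 1. If the last scan is before day 161, the subject cannot qualify through stable disease. A subject with a confirmed CR or PR, or with stable disease already at day 161, loses no CBR credit.
- *PFS (SAP 6.5.3).* Censored at the last evaluable RECIST assessment.
- *OS (SAP 6.5.5).* Censored at the last survival status date.

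**Which holds could cost CBR credit**

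Assumptions: the subject has stable disease throughout, the decision is made on the day the hold passes 21 days, and an End of Treatment (EOT) scan is done at the EOT visit and is the last scan.

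- Let the first held dose be on day h. Days h to h + 20 are 21 held days, so the hold passes 21 days on day h + 21.
- Section 7.1 places the EOT visit within 7 days of the decision, on days h + 21 to h + 28.
- Always short of the threshold: h + 28 < 161, so h ≤ 132. At h = 132, EOT falls on days 153 to 160.
- Never short: h + 21 ≥ 161, so h ≥ 140. At h = 140, EOT falls on days 161 to 168.
- For h = 133 to 139, the result depends on the EOT date.

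These bands depend on the EOT scan. Footnote 16 of the Schedule of Activities requires one only if no scan was done in the previous 4 weeks, and 8.1.1 allows extra scans. For example, with a hold from day 140, an extra scan on day 140 and EOT on day 161, the gap is 161 − 140 = 21 days. No EOT scan is required, and the last assessment is on day 140, below the threshold.

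**The case against.** The strongest reply is that this is loose wording which the rest of the protocol already corrects. Sections 7.1, 7.2, 7.6 and 9.4.5.4 all keep the subject in follow-up, and the sentence itself refers to 7.2. Harm requires a site to follow one sentence and overlook four sections. The rule can be waived with the Medical Monitor, and such holds should be uncommon. The palbociclib sentence may matter less still: SAP 5.2 treats Combination Phase 2 as a part that may not be executed, and CBR is only secondary in Combination Dose Escalation. Full data collection also had a cut-off of 18 May 2022 (SAP 8).

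All of this stands as a limit on size. It does not remove the contradiction. A site managing a long hold will look in the dose-adjustment section, and the instruction there is explicit.

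Two stronger readings are tempting but unsupported. A reader might infer that the sponsor intended to end follow-up for these subjects; the reference to 7.2 and the parallel toxicity rule point the other way. A reader might also infer that the first follow-up scan under 7.6 would have restored CBR credit for a given subject. Section 7.6 sets a 12-week interval but does not say whether it runs from the last dose, the EOT visit or the last scan, so no such scan date can be fixed from the documents.

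**Conclusion.** The contradiction is real and appears in two sections. Taken literally, the rule stops disease and survival follow-up for a reason unrelated to progression, and it can turn a subject with stable disease into a CBR failure. It should be corrected, but it is a small point.

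The documents do not support a claim that the primary result is materially biased. They give neither the number of non-toxicity holds over 21 days nor the chance that stable disease persists off drug. SAP 8 also drops the pooling behind the target of 75 subjects per dose level. No percentage-point effect on CBR can therefore be derived. The day bands show only which holds could matter, and only if the rule is applied literally and an EOT scan is done. They say nothing about how many such holds occurred.

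**What to change.** In 8.4.3.2 and 8.4.3.3, replace *removed from study* with *discontinued from study treatment*, and keep the exception that follows. Add one sentence to each: these subjects complete the EOT and Safety Follow-up visits and continue disease and survival follow-up per Sections 7.4 to 7.7.

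The wording should refer to study treatment as a whole. Stopping only the held drug would newly allow a combination subject to stay on ZN-c5 alone after a long non-toxicity palbociclib hold. Section 8.4.3.2 provides for single-agent ZN-c5 only after unmanageable adverse events attributed to palbociclib alone. That would be a change of treatment policy.

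The cost is one phrase and one sentence in two sections, plus slightly more follow-up for a few subjects at visits already scheduled. No new SAP output is needed: SAP 6.2 already summarises study discontinuations with their reasons, so the sponsor can look there for subjects who may have left under this rule. The rewording cannot recover data already lost.

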8.5 UNANTICIPATED PROBLEMS

8.5.1 DEFINITION OF UNANTICIPATED PROBLEMS (UP)

The Office for Human Research Protections (OHRP) considers unanticipated problems involving risks to participants or others to include, in general, any incident, experience, or outcome that meets all of the following criteria:

- Unexpected in terms of nature, severity, or frequency given (a) the research procedures that are
 described in the protocol-related documents, such as the IRB/IEC approved research protocol
 and informed consent document; and (b) the characteristics of the participant population being
 studied;
- Related or possibly related to participation in the research ("possibly related" means there is
 a reasonable possibility that the incident, experience, or outcome may have been caused by the
 procedures involved in the research); and
- Suggests that the research places participants or others at a greater risk of harm (including physical, psychological, economic, or social harm) than was previously known or recognized.

8.5.2 UNANTICIPATED PROBLEM REPORTING

The investigator will report unanticipated problems (UPs) to the reviewing IRB/IEC and the Sponsor. The UP report will include the following information:

- Protocol identifying information: protocol title and number, Pl's name, and the IRB/IEC project number;
- A detailed description of the event, incident, experience, or outcome;

- An explanation of the basis for determining that the event, incident, experience, or outcome represents an UP;
- A description of any changes to the protocol or other corrective actions that have been taken or are proposed in response to the UP.

To satisfy the requirement for prompt reporting, UPs will be reported using the following timeline:

- UPs that are serious adverse events (SAEs) will be reported to the IRB/IEC and to the study sponsor within the timelines for SAE reporting outlined in Section 8.3.6.
- Any other UP will be reported to the IRB/IEC and to sponsor within 15 business days of the investigator becoming aware of the problem.
- All UPs should be reported to appropriate institutional officials (as required by an institution's
 written reporting procedures), the supporting agency head (or designee), and the Office for
 Human Research Protections (OHRP) within 15 business days of the IRB/IEC's receipt of the
 report of the problem from the investigator.

8.5.3 REPORTING UNANTICIPATED PROBLEMS TO PARTICIPANTS

Not applicable.

9 STATISTICAL CONSIDERATIONS

9.1 STATISTICAL HYPOTHESES

For this study, all statistical analyses will be descriptive. No formal hypothesis testing will be performed.

For the Monotherapy and Combination Dose Escalation, statistical methodology will be applied towards identification of the MTD and for the Monotherapy and Combination Phase 2 setting towards estimation of anti-tumor activity.

Additional details on the planned statistical analyses may be found in the trial SAP.

9.2 SAMPLE SIZE DETERMINATION

9.2.1 MONOTHERAPY DOSE ESCALATION AND COMBINATION DOSE ESCALATION

The primary objective of this part of the study is to identify the MTD, if possible, or the RP2D of ZN-c5 as monotherapy and in combination with palbociclib, and to recommend dose(s) for evaluation in future clinical studies. Hence, the number of patients in the cohorts has been based on the desire to obtain adequate tolerability, safety and pharmacokinetic and pharmacodynamic data while exposing as few patients as possible to the investigational product and procedures.

For the Monotherapy Dose Escalation phase of the study, cohorts of 3-6 evaluable patients will be required. The total number of patients will depend upon the number of dose escalations necessary, but it is estimated to be approximately 36 subjects.

The Combination Dose Escalation with palbociclib will be initiated at a dose deemed well-tolerated in the Monotherapy Dose Escalation and proceed with higher ZN-c5 doses, as tolerated, based again on standard rules of a 3+3 design (Section 6.1.4). The total number of patients will depend upon the number of dose escalations necessary, but it is estimated to be approximately 40 subjects (including alternate dosing schedules, e.g., BID, and possible backfill). The subjects in the Combination Dose Escalation might also count towards the futility assessment stage accrual in the Combination Phase 2 (Section 6.1.7, Combination Phase 2).

9.2.2 MONOTHERAPY EXPANSION

The Monotherapy Expansion will be initiated at a dose selected based on PK, safety and any available biomarker data from the ZN-c5 Monotherapy Dose Escalation at a specific dose level will continue until a higher dose has been deemed to be well-tolerated (no DLTs in 3 subjects or at most 1 DLT in 6 subjects in the Monotherapy Dose Escalation), at which point expansion accrual might shift to the higher dose level.

The CBR as measured using RECIST v.1.1 will be assessed to provide preliminary anti-tumor activity evaluation in a patient population thought most likely to respond to ZN-c5.

The Monotherapy Expansion overall will target balanced accrual between the 3 lines of therapy (1st, 2nd and 3rd hormonal therapy line) across dose levels. The total cohort size necessary for futility has been estimated based on futility screening criteria targeting 10 evaluable subjects per line cohort at dose

levels where any anti-tumor activity is demonstrated and providing an acceptable false negative risk of concluding that there is no activity if the true clinical benefit rate is at least 40%.

Subjects are evaluable for the CBR if they have at least 1 post baseline disease/tumor assessment (Section 9.3). CBR as measured using RECIST v.1.1 will be assessed to provide preliminary anti-tumor activity evaluation in a patient population thought most likely to respond to ZN-c5. Data from these cohorts will provide a preliminary assessment of anti-tumor activity based on CBR.

The total number of patients in all expansion cohorts will depend upon the number of dose escalations, but it is not estimated to exceed 45 subjects.

9.2.3 MONOTHERAPY PHASE 2

Up to 3 dose levels with up to 75 subjects per dose level will be enrolled using a randomized (if 2 or more doses), parallel cohort, non-comparative (estimation) design.

Efficacy in the Monotherapy Phase 2 will be assessed as in the Monotherapy Expansion and CBR outcomes in the Monotherapy Phase 2 will be combined with those from subjects in the Monotherapy Expansion arm who were treated with ZN-c5 as $2^{nd}/3^{rd}$ Line of treatment and dosed at the same ZN-c5 dose in the Monotherapy Expansion. The sample size is determined in order to estimate the CBR at each dose level with certain confidence before proceeding with a larger confirmatory study. Based on the targeted sample size, the precision for a 95% exact confidence interval around a hypothesized 40-50% CBR rate is \pm 12% at each dose level studied.

Historical estimates for the CBR rate specific to $2^{nd}/3^{rd}$ Line patients (either post CDK4/6 inhibitor or not) are not readily available. The CBR range was estimated based on two studies, reporting a CBR rate for fulvestrant alone of 40% in 2^{nd} Line or higher (PALOMA-3) and 56% CBR in 1^{st} or 2^{nd} Line (MONARCH-2). The targeted precision will be adequately achieved within the specified range and it will increase further outside of the range, if the true CBR rate is further (higher or lower) from 50%.

9.2.4 COMBINATION PHASE 2

The Combination Phase 2 portion follows a randomized, parallel group, non-comparative design, assuming both the RP2D and the lower dose are investigated, or a single dose cohort, if only the RP2D is investigated. Each dose cohort is independently powered (non-comparative) and follows a Simon 2-stage design.

Approximately 56 subjects will be enrolled in each dose cohort. Subjects treated in the Combination Dose Escalation at lower doses can possibly also count towards the futility stage accrual, assuming the subjects are evaluable. The two dose cohorts evaluated in Phase 2 will not use the same subjects from lower dose cohorts in the Phase 1 Combination Dose Escalation phase; for example, ZN-c5 50 mg Combination Dose Escalation subjects may count for the 100 mg futility cohort in Phase 2, if that is selected as the lower dose cohort for the Phase 2 component but will not also count for the RP2D futility cohort, if a higher dose is selected as the RP2D.

CBR as measured using RECIST v.1.1 will be assessed to provide preliminary anti-tumor activity evaluation in a patient population thought most likely to respond to ZN-c5. Subjects are evaluable for CBR if they have at least 1 post baseline disease/tumor assessment (Section 9.3).

Sample size for each dose cohort is based on a Simon 2-stage design with 80% power at the 1-sided 2.5% alpha level to differentiate between 50% CBR (poor performance) and 70% CBR (promising performance). Fifty-one (51) evaluable subjects will be enrolled in two stages, with 19 subjects in Stage 1 and 32 subjects in Stage 2. The probability of early stopping is 68%. The Combination Phase 2 will target balanced accrual between the 2 lines of prior hormonal therapy (1st and 2nd hormonal therapy line) across dose levels.

Second stage accrual will be completed, assuming that Stage 1 futility criteria are exceeded with at least 11 subjects with CBR in the first 19 evaluable subjects. An approximate 10% loss for CBR evaluability has been assumed resulting in a sample size of approximately 56 subjects for each cohort, resulting in a total sample size of approximately 112 subjects for this trial stage.

